7.7 Dose Modifications

There are no planned dose modifications or delays except as detailed in section 7.5 in association with the IL-2 administration.

Note: If patients required dose modification of IL-2 during course 1 then the modified dose should be used for course 2.

7.8 Management of Selected Toxicities Associated with NK Cell Infusion

See Appendix VII for expected toxicities of Decitabine, Vorinostat and Interleukin-2.

7.8.1 Acute Allergic Reaction Secondary to the Infusion of Allogeneic NK Cells

Although infusion of donor lymphocytes has not been associated with acute allergic reactions, patients will be closely watched for the occurrence of hypotension, dyspnea and angioedema during and immediately after the infusion.

The NK cell infusion will be stopped if severe acute reactions occurs (defined as CTCAE grade 4 - life-threatening consequences; urgent intervention indicated). A blood sample will be collected for HAMA testing per section 8.1.3.

7.8.2 Vascular Leak Syndrome

Neither administration of allogeneic NK cells nor autologous IL-2 activated NK infusions have been associated with vascular leak syndrome in our previous experience. Nevertheless, patients will be monitored for weight gain (by weights at least 3 times per week) and pulmonary edema during IL-2 administration.

7.8.3 Tumor Lysis Syndrome

Allopurinol will be initiated to according to standard medical practice when the risk of tumor lysis is high.

7.8.4 Prolonged Marrow Suppression

Hematologic toxicity due to allogeneic NK cells may occur later, and therefore hematologic recovery will be assessed beyond the expected chemotherapy-induced nadir.

Pancytopenia will occur with this regimen and should be treated as follows:

Anemia and thrombocytopenia are expected in all patients, and they will receive standard supportive transfusion care according to transfusion committee guidelines or as modified based on clinical parameters. Prolonged anemia or thrombocytopenia are not unexpected and will not count towards toxicity.

Neutropenia is expected in the majority of patients, and they will receive supportive care with prophylactic antibiotics as noted below. G-CSF and granulocytes should be avoided unless clinically indicated in the setting of severe, uncontrolled infection. If the clinical situation warrants growth factor use, then any remaining IL-2 administration will be stopped.

7.9 Supportive Care Guidelines/Concomitant Medication Use

Patients will receive standard supportive care according to institutional guidelines or as modified based on clinical parameters.

Antiemetics will be used according to standard medical practice. Given the modest incidence of nausea, diarrhea, and anorexia with the drug combination, scheduled prophylactic antiemetics will be given during Day 1-15 of therapy.

All patients will receive antibacterial prophylaxis and antifungal therapy while neutropenic (until ANC >1000 x 2 days). Antibacterial options include but are not limited to levofloxacin, azithromycin, Pen V K and antifungal options include fluconazole, voriconazole, posaconazole as indicated. Choice of antibiotics is left to the discretion of the treating physician. Antiviral therapy and trimethoprim/sulfa for PCP prophylaxis are not required unless clinically indicated.

7.10 Duration of Therapy

Patients will receive two courses of study treatment unless one or more of the following occurs:

- Patient withdraws consent or is non-compliant
- Criteria in section 7.6 for a 2nd treatment course are not met
- Medically unsafe, in the opinion of the treating investigator to continue with the treatment plan and based on development of grade 4 non-hematologic toxicities

- Intercurrent illness that prevents further administration of treatment
- Unacceptable toxicity
- Evidence of rapid disease progression defined as $\geq 20\%$ peripheral blood blast percentage suggesting progression to acute leukemia

Any patient who discontinues therapy before the completion of 2 courses should have a bone marrow biopsy and aspirate performed at the time treatment is discontinued. Those who are not evaluable per section 13 will be followed only until the resolution or stabilization of treatment related toxicity. No further follow-up for this study will be required, other than recording the date and cause of death upon knowledge in OnCore.

7.11 Follow-up

All evaluable patients will be followed for response and survival for 1 year from study enrollment unless the patient withdraws consent.

Ongoing therapy with maintenance hypomethylating agents or proceeding to allogeneic stem cell transplantation will be at the discretion of the patient's primary oncologist.

For patients completing 1 year of follow-up no further data collection will be required for this study; however the date and cause of death will be entered in OnCore upon knowledge for IND annual reporting.

An exception to this for all patients is the reporting upon knowledge of any serious, unexpected and at least possibly study treatment related event per sections 11.3 and 11.4.

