- Therapy related MDS
- Severe cytopenias: Severe neutropenia (ANC \leq 0.8), platelet or PRBC transfusion dependent
- WHO Based Prognostic Scoring System (WPSS): High or Very High Risk

Prior treatment:

- Untreated/Minimally Treated: May be untreated or have had a maximum of 2 previous cycles of hypomethylating agents (azacitidine or Decitabine) **without** evidence of treatment failure
- Treatment Failure: Patients who have not responded to or whose disease has progressed on hypomethylating agents (azacitidine or decitabine), 7+3 type induction chemotherapy, or immunosuppressive therapy such as ATG+CSA

Age \geq 18 years of age, ECOG 0-2, adequate renal, hepatic and cardiac function as defined in section 4.6
Available related HLA haploidentical NK cell donor age 18-75 years

[figure not shown]
Accrual Objective:

Stage 1 – 15 evaluable patients; Stage 2 activate if \geq 6 of stage I patients achieve response. If so, then enroll an additional 31 patients for a total of 46 evaluable patients

Study Schema

Treatment Plan:

All treatment to be administered as an outpatient

Decitabine 10 mg/m² IV over 1 hour days 1-5

Vorinostat 200 mg PO twice a day days 6-15

IL-2 activated donor NK cell infusion IV over 15 to 60 minutes day 17

IL-2 6 MU SQ for 3 doses beginning on day 17 (2 hours after NK cell infusion), then day 19 and day 22

- Repeat treatment course 6 to 8 weeks later unless unacceptable toxicity, medically unsafe, or evidence of rapid disease progression as defined in section 7.10
- Assess for disease response 4 to 6 weeks after 2nd treatment course
- Follow for survival and progression to AML for 1 year from enrollment

* A single donor apheresis will be collected on day 15 of course 1. Centralized cell processing will occur at the University of Minnesota utilizing overnight shipping for Mayo products (U of MN products will be held an extra 24 hours to match Mayo's timing). The NK cell product will be divided in two after processing, but before IL-2 activation. Half will be stored frozen until course 2. The remaining cells will be prepared for fresh administration on day 17 of course 1.

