11.2 Adverse Event Documentation

Adverse events occurring after the initiation of any study treatment must be documented. Adverse events attributed to a study-related procedure which occur prior to the initiation of study treatment must be documented as well. Refer to appendix VII for a list of expected toxicities.

For the purposes of this study, adverse event documentation requirements will be determined based on grade, expectedness and relationship to study therapy as follows:

	Grade 1	Grade 2		Grade 3		Grade 4 and 5
	Expected or Unexpected	Expected	Unexpected	Expected	Unexpected	Expected or Unexpected
Unrelated Unlikely	Not required	Not required	Not required	Not required	Required	Required
Possible Probable Definite	Not required	Not required	Required	Required non-hematological	Required	Required
				Not required - hematologic events		

All patients will be monitored from the initiation of any study treatment through day 45 after the last dose of study treatment or the start of a new treatment, whichever occurs earlier, as it is expected that most treatment related adverse events will occur during this period. However, the investigator is obligated, upon knowledge of, to report any adverse event considered to be related to study treatment meeting the expedited reporting criteria in section 11.4.

In addition, adverse event collection will include targeted adverse events and unexpected adverse events at specific time points in relation to the NK cell infusion and post NK cell infusion IL-2 injections.

Targeted adverse events (Appendix IX) and unexpected events will be collected at the following time points. Adjust the day to match the time point description. All time points are 24 hours +/- 2 hours.

- Post-Chemo/Pre-NK cell infusion (day 17)
- A single assessment 1-2 hours post NK cell infusion/pre IL-2 injection (day 17)
- pre IL-2 dose 2
- pre IL-2 dose 3
- 48 hours post IL-2 dose 3 (or to coincide with day 24 clinic visit)
- 1 week after last IL-2 dose (or to coincide with day 31 clinic visit)

At each time point, the worst grade of the targeted toxicity since the last assessment or the previous 24 hours (whichever is shorter) will be recorded in addition to any unexpected toxicities felt at least possibly related to the NK cells and/or the IL-2.

In addition, although not always a reportable event, deaths will be recorded in OnCore upon knowledge in the follow-up tab.

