13.0 Statistical Considerations

13.1 Simon's Two-Stage Design and Sample Size

This is a single clinic Simon's optimum two-stage phase II clinical trial designed to determine the objective response rate (CR+PR+HI) after two courses of Decitabine and Vorinostat with haploidentical NK cells in patients with high risk MDS. The null hypothesis of the study is $P_{R0} \leq 0.30$ and alternative hypothesis is $P_{R1} \geq 0.50$. Based on this design and the assumption that the majority of patients will complete both cycles of therapy, a maximum of 46 evaluable patients will be used which is sufficient to maintain an overall type I error 5% while providing 80% statistical power.

In the first stage 15 patients will be enrolled, the trial will be terminated if 5 or fewer respond. If 6 patients respond, then the trial goes on to the second stage, and 31 more patients will be studied. If the total number responding is less than or equal to 18, then this approach will be deemed unworthy of further study.

Considering a predicted dropout rate of 10% during the two courses of therapy, in order to have 15 or 46 patients evaluable for the response rate, we will need a maximum of 17 patients (if the study is stopped by 1st stage) or 51 patients (if the study proceeds to 2nd stage).

Only patients completing both course 1 and 2 of planned therapy will be evaluable for response. However, all the patients with complete or partial treatment will be included in the evaluation for toxicities.

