13.3 Statistical Analysis Methods

Ninety-five percent confidence intervals for the response probability were calculated using methodology reported by Duffy and Santner.⁴⁰

The summary statistics including 95% confidence intervals for toxicity rate and proportion of patients who become transfusion independent will be calculated. The association of in vivo NK cell expansion, as defined as persistence of donor NK cell chimerism at day +8, (yes or no) with clinical response will be estimated by chi-square test. Kaplan- Meier method will be used to estimate 1- year survival from the date of treatment. Given that the majority of patients will go on to receive additional therapy with either ongoing hypomethylating agents versus stem cell transplant, the estimates of 1 year overall survival from the point of study enrollment, will only be partially attributable to the study therapy and thus a minor focus of our statistical analysis.

SAS 9.2 (Cary, NC, USA) will be used for statistical analyses.

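### One-year overall survival has no defined analysis set, two time origins, and required follow-up only for patients who complete both courses

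*Combined protocol and SAP*

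**What the plan says.** One-year overall survival (OS) is a secondary objective (Synopsis and section 1.2). Five places decide who contributes to it.

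- **Section 7.11:** "All evaluable patients will be followed for response and survival for 1 year from study enrollment unless the patient withdraws consent".
- **Section 7.10**, on patients who stop before finishing two courses: "Those who are not evaluable per section 13 will be followed only until the resolution or stabilization of treatment related toxicity". It continues: "No further follow-up for this study will be required, other than recording the date and cause of death upon knowledge in OnCore".
- **Section 13.1**, the only place in section 13 that defines evaluable: "Only patients completing both course 1 and 2 of planned therapy will be evaluable for response". The sentence after it puts fully and partly treated patients in the toxicity evaluation. No set is named for OS.
- **Study Schema**, with no restriction to evaluable patients: "Follow for survival and progression to AML for 1 year from enrollment". The calendar in 8.1.1 likewise has an unrestricted survival-status row at Days 90, 180, 270 and 360.
- **Section 13.3:** the Kaplan-Meier "method will be used to estimate 1- year survival from the date of treatment". A later sentence speaks of "the estimates of 1 year overall survival from the point of study enrollment" and calls OS a minor focus, because later therapy clouds attribution.

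Active observation of early stoppers is otherwise limited to adverse-event monitoring under section 11.2: "All patients will be monitored from the initiation of any study treatment through day 45 after the last dose of study treatment". It ends sooner if new treatment starts.

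**The concern.** The patients released from follow-up are not a random subset. Section 7.10 lists rapid progression, unacceptable toxicity and intercurrent illness among the reasons for stopping, and section 6.2 replaces patients who stop. A set limited to followed patients therefore fills with people who lived through both courses. Both stated origins come before that point, so each completer carries a stretch of guaranteed survival.

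Adding the early stoppers back at analysis does not fully repair this. Their later deaths are counted if they become known, while the others are censored when observation ends. Censoring then depends on outcome. The estimate is too high if deaths are missed. It can be too low if deaths are found but survivors are not confirmed alive.

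Two analysts working from this plan could report different OS figures and both claim to follow it. Two sites could also follow different patients, depending on whether they work from the schema or from 7.10 and 7.11.

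**Working it through.** The plan states no OS rate, so there is no OS figure to reproduce. Survival rates below are assumptions: 60% at one year in completers, and 0%, 20% or 40% in early stoppers.

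**1. Share outside required follow-up.** Section 13.1 assumes 10% dropout and gives 46 evaluable of 51 enrolled. 46 / 0.9 = 51.1, which agrees (strict rounding up would give 52, which is immaterial here). The excess is 46 / 0.9 - 46 = 5.1, so about 5 patients. At 20% dropout it would be 46 / 0.8 - 46 = 11.5, about 12.

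**2. Guaranteed survival in completers.** Course 2 starts 42 to 56 days after course 1 starts (section 7.6), and its day 22 falls 21 days later. 42 + 21 = 63 and 56 + 21 = 77 days, or 9 to 11 weeks.

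**3. End of active observation for a patient who stops after course 1.** Last IL-2 on day 22, plus 45 days (section 11.2), is day 67 at the latest. The first survival check is targeted at Day 90.

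**4. Completers-only estimate.** All-treated OS = (1 - d) x 0.60 + d x (stopper OS).

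| Dropout d | Stopper OS 0% | 20% | 40% | Completers only | Overstatement |
|---|---|---|---|---|---|
| 10% | 54% | 56% | 58% | 60% | 6, 4, 2 points |
| 20% | 48% | 52% | 56% | 60% | 12, 8, 4 points |

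**5. Early stoppers included, deaths captured passively (d = 10%).** Let G(t) be stopper survival at day t and q the share of their deaths after day 67 that become known. All other stoppers alive at day 67 are censored then. No completer dies before that day. In large samples Kaplan-Meier at one year is

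S = [0.9 + 0.1 G(67)] x 0.54 / [0.9 + 0.1 q (G(67) - G(365))],

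where 0.54 = 0.9 x 0.60. With exponential stopper survival, G(67) is 0.2^(67/365) = 0.744 or 0.4^(67/365) = 0.845. With deaths uniform over the year in the 0% case, it is 1 - 67/365 = 0.816.

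| Stopper OS | True OS | q = 0 | q = 0.5 | q = 1 | Error (points) |
|---|---|---|---|---|---|
| 0% | 54.0% | 58.9% | 56.3% | 54.0% | +4.9, +2.3, 0.0 |
| 20% | 56.0% | 58.5% | 56.7% | 55.1% | +2.5, +0.7, -0.9 |
| 40% | 58.0% | 59.1% | 57.6% | 56.3% | +1.1, -0.4, -1.7 |

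For example, at 20% and q = 0: 0.9744 x 0.54 / 0.9 = 0.585. A simulation with 1,000,000 patients agrees with these values to about 0.1 point.

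**6. Sensitivity to the censoring day.** Sections 11.3 and 11.4 end reporting at day 45 of the last course, and section 13.2 also ends toxicity assessment two weeks after the last dose (22 + 14 = day 36). For stopper OS of 20% and q = 0, day 45 gives 0.6 x [0.9 + 0.1 x 0.2^(45/365)] = 58.9%, and day 36 gives 59.1% by the same formula. Both compare with 58.5% at day 67.

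**7. Time origin.** Assume 7 to 28 days (g) between enrollment and first dose, a constant hazard, and no deaths in the gap, since patients who never start are removed under section 6.2. The difference is S^((365-g)/365) - S. It ranges from 0.5 points (S = 70%, g = 7) to 2.9 points (S = 40%, g = 28).

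**8. Sampling error for scale.** 1.96 x sqrt(0.6 x 0.4 / 46) = 0.142, a half-width of about 14 points.

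**The case against.** - **The schema and calendar are summaries.** Both set out the path of a patient who finishes treatment, so they may be incomplete rather than contradictory. That is a fair reading, but it leaves 7.10 and 7.11 in force, and those sections create the gap.
- **Section 13.1 defines evaluable for response, not for survival.** True. However, section 7.10 itself points to section 13 to decide who leaves follow-up, and no other definition exists there.
- **The origin is settled by the method sentence.** Enrollment appears only in the caveat about attribution, and step 7 shows a small effect. This part alone would be a wording correction.
- **Day 67 is one of several readings.** Correct. Section 7.10's own end point, resolution or stabilization of toxicity, could fall earlier or later. Step 6 shows that the earlier dates move the estimate by well under one point.
- **The effect is small and OS is a minor focus.** At planned dropout the error is below sampling error, every survival rate is assumed, and no decision rule uses OS. This stands and limits the weight of the point. The plan's reason for the minor focus concerns attribution to study therapy, though, and does not settle who is counted or from when.
- **Vital status may be recoverable.** Section 12.5 keeps a log that allows retrieval of medical records. That could reduce the loss, but the plan does not require such a search, and records may not show the outcome of patients treated elsewhere.

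**Conclusion.** The concern holds. Followed as written, sections 7.10 and 7.11 leave vital status incomplete for the patients likely to do worst, and section 13.3 does not say who enters the OS estimate or fix one starting point.

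Under the assumed survival rates and the planned 10% dropout, a completers-only analysis is certain to overstate OS, whereas passive capture in all treated patients can err in either direction. The completers-only error doubles if dropout reaches 20%, which is above the plan. The direction in a completers-only analysis requires only that early stoppers survive less well than completers. The sizes depend on the assumed rates. The plan should be corrected on this point, but nothing in the primary analysis or the stopping rules turns on it.

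**What to change.** 1. In 7.10 and 7.11, follow every patient who receives a first dose of decitabine for vital status to one year from that dose, unless consent is withdrawn. Record review or patient contact is enough, as footnote 7 of the calendar already allows.
2. Bring the schema and the calendar into line with that wording and clock. The last check is targeted at Day 360 with a four-week window, so it should establish status for the full year.
3. In 13.3, define the OS set as all treated patients, with the first decitabine dose as the single origin.
4. If a completers analysis is kept, label it a landmark analysis starting at the end of course 2.

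The cost is vital-status checks at the four scheduled times for about 5 more patients at the planned dropout, or about 12 if dropout reaches 20%. No visits or procedures are added. The consent text is not available here and may need a matching sentence. The OS estimate may come out less favourable.

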8.0 Study Calendar

The pre-treatment work-up must occur within 28 days (14 days for CBC, diff, CMP, and chemistries) of treatment start unless otherwise noted. Scheduled evaluations (including research samples) up to day +22 may be performed +/-1 day from the targeted date; evaluations and procedures (including research samples) performed after day +28 may be done +/-3 days of the targeted date. Follow-up for survival may be done +/- 4 weeks of the targeted date. In addition, targeted days may be altered as clinically appropriate.

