1.2 Secondary Objectives

- Assess the safety and tolerability of Decitabine and Vorinostat followed by an infusion of CD3-/CD19- donor NK cells and a short course of IL-2 when given in the outpatient setting in patients with high risk MDS
- Assess the proportion of patients who become transfusion independent (red blood cells and/or platelets)
- Estimate the association of in vivo NK cell expansion with clinical response
- Estimate 1 year Overall Survival (OS)

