8.1 Patient

8.1.1 Standard of Care and Investigational Treatment

	Pre-Treatment (within 28 days of treatment start)*	During each treatment course					4-6 weeks after 2 nd treatment course	Follow-up at Day 90, 180, 270, 360	
		Day 1 ¹	Day 5	Day 15 or 17	During IL-2 administration (Day 17-22)	Day 24, 31, 38, 45			
EVALUATIONS									
Written consent	X								
Medical history	X								
Disease Characteristics	X								
Pathology review of outside dx	X								
Transfusion History	X						X		
Concomitant meds	X	X					X		
Physical exam	X	X	X ⁶	X ⁶	X ⁶	X ⁶	X		
Vital signs	X	X		X					
Weight	X	X		X	3 x a week during IL-2	X			
Height	X								
ECOG Performance Status	X	X					X		
Survival Status								X ⁷	
LABORATORY									
CBC w/ diff ²	X	X	X	X	daily during IL-2	X	X		
Na, K, Cl, CO ₂ , BUN, creatinine, uric acid, phos, LDH, Mg	X	X	X	X		X			
ALT/AST, bili, total protein, albumin, alk phos	X	X		X		X			
Chest X-ray	X								
INR/PTT	X								
Pregnancy test ³	X								
HLA typing (low resolution)*	X								
Recipient Viral Serology	X								
ECHO/MUGA*	X								
Bone Marrow Bx/Asp ⁴	X ⁴					X ⁵	X ⁴		
Investigational TREATMENT									
Decitabine IV		Day 1-5							
Vorinostat PO			Day 6-15						
NK cell infusion (research)				Day 17					
IL-2 tiw for 3 doses (research)					X (start Day 17)				

* CBC, dff, CMP, chemistries within 14 days of study treatment start, HLA typing may be done at any time

- 1- Course 1 Day 1 evaluations need not be repeated if pre-study evaluations were done within 14 days of 1st treatment
- 2- CBC with diff weekly throughout all treatment with increased frequency as clinically indicated
- 3- Women of childbearing potential only; serum or urine
- 4- Bone marrow aspirate and biopsy with standard flow cytometry, conventional cytogenetics, and MDS/AML FISH panel will be conducted at study initiation and at the completion of the 2nd cycle for standard disease assessment or at time of study withdrawal if early termination.
- 5- Prior to course 2 ONLY in patients who enrolled in this study as a prior treatment failure per section 4.2.2 or any patient who is discontinuing study treatment after 1 course
- 6- Clinical assessments will occur at a minimum of weekly up until the NK cell infusion on Day +17 after which clinical assessments will occur daily until the day after the final IL-2 administration.
- 7- By record review, patient contact, etc.

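### The last survival contact (Day 360 +/- 4 weeks) can fall before 1 year with none required later, and the calendar has no item for the AML and response follow-up promised for that year

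*Combined protocol and SAP*

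**What the plan says.** One-year survival is a listed secondary objective in section 1.2 ("Estimate 1 year Overall Survival (OS"). Section 13.3 gives the method: "Kaplan- Meier method will be used to estimate 1- year survival from the date of treatment". A later sentence in the same section counts from enrollment instead, and calls survival a minor focus because most patients will go on to other therapy.

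Follow-up is promised in two places. The Study Schema says: "Follow for survival and progression to AML for 1 year from enrollment". Section 7.11 says: "All evaluable patients will be followed for response and survival for 1 year from study enrollment".

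The calendar in section 8.1.1 delivers this through one column, "Follow-up at Day 90, 180, 270, 360". Only the Survival Status row is marked in it, with the footnote "By record review, patient contact, etc". Section 8.0 sets the tolerance: "Follow-up for survival may be done +/- 4 weeks of the targeted date". Nothing is scheduled after Day 360. Sections 7.11 and 11.2 have deaths entered in the database when the site learns of them.

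**The concern.** A Kaplan-Meier estimate at 1 year is best supported when survivors are still under observation at 1 year. Here the target of the last contact is already 5 days short of day 365 from treatment start, and the window allows it to be 33 days short. A survivor contacted on target or early is censored before the time point of interest, and no later contact brings that patient back into the risk set. Deaths are treated differently: one that comes to light after an early contact can still be entered. Deaths and survivors would then be followed to different dates.

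The second issue is a mismatch within the protocol. Two passages promise a year of follow-up for AML progression and for response, but the follow-up column has no item for either, and none for the later therapy that section 13.3 says will affect survival. At stake are the quality of a secondary estimate and the ability to report AML progression or put the survival figure in context.

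**Working it through.** The plan states no sample size, precision or expected rate for 1-year survival, so there is no figure to reproduce. The true rate and the constant hazard below are assumptions. Calendar Day n is treated as n days from treatment start.

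**Window.** Target Day 360 and 4 weeks either side (sections 8.1.1 and 8.0): 360 - 28 = 332 and 360 + 28 = 388. Shortfall from day 365: 365 - 332 = 33 days at the earliest, and 365 - 360 = 5 days on target.

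**Survivors censored before day 365.** With contacts spread evenly over the window: (365 - 332)/(388 - 332) = 33/56 = 59%, leaving 41% at risk. With all contacts on target, 100% are censored.

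**Bias when no late deaths are added.** With a constant hazard, S(t) = S(365)^(t/365). If every contact is on day t, the curve is carried forward from t:

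| Assumed S(365) | S(332) | Overstatement | S(360) | Overstatement |
|---|---|---|---|---|
| 0.40 | 0.4345 | 3.5 points | 0.4051 | 0.5 point |
| 0.50 | 0.5323 | 3.2 points | 0.5048 | 0.5 point |
| 0.60 | 0.6284 | 2.8 points | 0.6042 | 0.4 point |

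**Numbers at risk and precision.** Simulated Kaplan-Meier estimates for 46 patients at assumed S(365) = 0.50 (4,000 runs):

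| Last contact | Mean estimate | SD | Mean number at risk at day 365 |
|---|---|---|---|
| Followed past day 365 | 0.502 | 0.074 | 23.1 |
| Spread evenly, Days 332-388 | 0.503 | 0.076 | 9.5 |
| All on Day 360 | 0.504 | 0.073 | 0 |
| All on Day 332 | 0.534 | 0.072 | 0 |

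Even spread more than halves the number at risk and raises the SD only slightly. In the last two rows the SD is no larger, but the estimate is really of survival at Day 360 or Day 332.

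**Effect of late-learned deaths.** Take the extreme case in which every death up to day 365 is entered while survivors stay censored at last contact (46 patients, S(365) = 0.50).
- All contacts on Day 360: each patient has probability 0.5048 - 0.5 = 0.0048 of dying between Day 360 and day 365. The chance of at least one such death is 1 - (1 - 0.0048)^46, about 20%. When one occurs, only patients who die are left in the risk set, and the curve drops to zero. The mean estimate is about 0.40.
- Contacts spread evenly: the mean is about 0.485, or 1.5 points low.

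These are upper limits, since not every late death would come to the site's notice.

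**Disease follow-up.** Course 2 starts 6 to 8 weeks after course 1 (section 7.6), about Day 43-57. The response assessment follows 4 to 6 weeks later:
- Counted from the start of course 2: 43 + 28 = 71 to 57 + 42 = 99.
- Counted from its last IL-2 dose, 21 days after the course starts: 64 + 28 = 92 to 78 + 42 = 120.

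The rest of the promised year is 365 - 120 = 245 to 365 - 71 = 294 days. No AML or response item is scheduled in that time.

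**The case against.** The strongest reply is that section 7.11 is the governing rule: it requires survival follow-up for a full year, and the 4-week window is only a scheduling tolerance. Status can come from record review and may be confirmed as late as Day 388. This stands in part, because early censoring is permitted rather than required. But a general duty to follow for a year does not place a survivor at risk at day 365 when the last required contact comes earlier.

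The time origin also matters. If survival is counted from enrollment and enrollment is a week before Day 1 (an assumption), Day 360 is 367 days from enrollment and already past 1 year. Day 332 would be 339 days. Even with enrollment a full 28 days before treatment, Day 332 would be 360 days, still short. So the statement that on-target contacts fall short holds for the treatment-start origin only.

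Size is a fair objection too. At S = 0.50 the approximate 95% half-width is 1.96 x sqrt(0.25/46), about 14 points, or 25 points with 15 patients. A bias of 0.5 to 3 points is small beside that. No decision rests on survival.

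A reader might infer that the 1-year estimate is bound to be about 3 points too high, or that hardly anyone will be under observation at 1 year. The documents do not support either. Day 332 for every patient is the worst case the window allows, and with even spread 41% of survivors remain at risk with almost no bias. Nor can deaths after 1 year distort S(365); only deaths between an early contact and day 365 can.

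A reader might also infer that AML and response are never assessed, or that a planned analysis is lost. Response is formally assessed, with marrow, after course 2, which is the primary endpoint. Time to AML and duration of response are not listed endpoints. The gap is in later follow-up, and it is read from the calendar; the case report forms are not in the documents and may hold more.

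**Conclusion.** The point holds as a modest weakness in a secondary endpoint and an inconsistency in the protocol. The schedule permits the last survival contact before 1 year and requires none after it. The main consequence is thin support for the estimate at 1 year. The direction of any bias depends on how contacts fall and on whether late deaths are entered: from about 3 points high in the worst case without late deaths, through roughly zero, to a downward error if deaths are added while survivors stay censored. That downward error is small when contacts are spread evenly but can be large when contacts cluster at or before Day 360. These sizes rest on a constant hazard and an assumed 1-year survival of 40-60%, counted from treatment start.

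The AML and response promises do not match the survival-only follow-up column and need reconciling. Neither issue touches the response-rate conclusion.

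**What to change.** 1. State one time origin for overall survival in section 13.3, and require the final vital-status check on or after 1 year from it, for example Day 365 with a window of 0 to +4 weeks. Keep +/- 4 weeks at Days 90, 180 and 270.
2. At the four existing record-review contacts, also record the date of progression to AML and the start date and type of the next MDS therapy, including transplant.
3. Either record response status from the chart at these contacts, or delete response follow-up from section 7.11.

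The cost is a last contact that may fall up to 4 weeks after 1 year, plus a few chart-review fields. No new visit or procedure is needed.
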